## 14.3.12 Evaluation of overall lesion response

The evaluation of overall lesion response at each assessment is a composite of the target lesion response, non-target lesion response and presence of new lesions as shown below in Table 19.

Table 19: Overall lesion response at each assessment

Target lesions	Non-target lesions	New Lesions	Overall lesion response
CR	CR	No	$CR^1$
CR	Non-CR/Non-PD	No	$PR^2$
CR	UNK	No	PR
PR	Non-PD and not UNK	No	$PR^{1,2}$
SD	Non-PD and not UNK	No	$SD_1$
UNK	Non-PD	No	UNK 
PD	Any	Yes or No	PD
Any	PD	Yes or No	PD
Any	Any	Yes	PD

This overall lesion response also applies when there are no non-target lesions identified at baseline.

If the evaluation of any of the target lesions identified at baseline could not be made during follow-up, the overall status must be 'unknown' unless progression was seen.

In some circumstances it may be difficult to distinguish residual disease from normal tissue. When the evaluation of complete response depends on this determination, it is recommended that the residual lesion be investigated (fine needle aspirate/biopsy) to confirm the CR.

Unconfirmed PR will be considered SD for analysis purposes. If there are no baseline scans available at all, then the overall lesion response at each assessment should be considered Unknown (UNK).

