## 7.2 Assessment types

## 7.2.1 Efficacy assessment

Tumor response will be evaluated locally by the investigator according to the guideline (see Appendix 3) based on the Response Evaluation Criteria in Solid Tumors (RECIST) Version 1.1 (Eisenhauer 2009). Each patient will be evaluated for all potential sites of tumor lesions at screening/baseline and every 8 weeks after starting study treatment until disease progression.

CT (Computed Tomography) /MRI (Magnetic Resonance Imaging) scans will be performed at baseline within 28 days before start of treatment and subsequently every 8 weeks from treatment start until progression of disease.

After baseline, the first assessment should be performed at Cycle 3 Day 1 ( $\pm$ 7 day window) and all subsequent assessments should be performed within  $\pm$ 7 days of the scheduled day of assessment. The same method of assessment and the same technique should be used to characterize each individual and reported lesion at baseline and during follow-up. If a patient discontinues treatment for reasons other than radiological documentation of progression of disease, an efficacy assessment should be performed at the time of End of Treatment unless a CT/MRI for tumor measurement was performed  $\leq$  4 weeks earlier.

Chest, abdomen, and pelvis CT scans are required for all patients at baseline. If at baseline, a patient is known to have a contraindication to CT i.v. contrast media or develops a contraindication during the trial, a contrast-enhanced MRI (if possible) of chest, abdomen, and pelvis should be performed. CT/MRI of the brain should be performed if clinically indicated.

For the patients with skeletal lesions suspected at baseline, whole-body bone imaging should be obtained either with a TC99 bone scan or alternatively a NaF CT/ MRI PET scan. Of note, the CT or MRI portion of the scan should only be substituted for the required chest, abdomen, and pelvic CT scans if the CT or MRI is of diagnostic quality and meets all requirements as described in the study imaging guide (ie, oral and IV contrast, slice thickness, and anatomic coverage). Post-baseline, if skeletal lesions were identified at baseline, which are not visible on the chest, abdomen or pelvis CT/MRI scan, bone imaging with either a TC99 bone scan or NaF CT/MRI PET is required at all post-baseline imaging timepoints (every 8 weeks). In all cases that post-baseline bone

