# 14.3.3 Methods of tumor measurement - general guidelines

In this document, the term "contrast" refers to intravenous (i.v.) contrast.

The following considerations are to be made when evaluating the tumor:

- All measurements should be taken and recorded in metric notation (mm), using a
  ruler or calipers. All baseline evaluations should be performed as closely as possible
  to the beginning of treatment and never more than 4 weeks before the beginning of
  the treatment.
- Imaging-based evaluation is preferred to evaluation by clinical examination when both methods have been used to assess the antitumor effect of a treatment.
- For optimal evaluation of patients, the same methods of assessment and technique should be used to characterize each identified and reported lesion at baseline and during followup. Contrast-enhanced CT of chest, abdomen and pelvis should preferably be performed using a 5 mm slice thickness with a contiguous reconstruction algorithm. CT/MRI scan slice thickness should not exceed 8 mm cuts using a contiguous reconstruction algorithm. If, at baseline, a patient is known to have a medical contraindication to CT contrast or develops a contraindication during the trial, the following change in imaging modality will be accepted for follow-up: a noncontrast CT of chest (MRI not recommended due to respiratory artifacts) plus contrast-enhanced MRI of abdomen and pelvis.
- A change in methodology can be defined as either a change in contrast use (e.g. keeping the same technique, like CT, but switching from with to without contrast use or vice-versa, regardless of the justification for the change) or a change in technique (e.g. from CT to MRI, or vice-versa), or a change in any other imaging modality. A change in methodology will result by default in a UNK overall lesion response assessment. However, another response assessment than the QED Therapeutics calculated UNK response may be accepted from the investigator or the central blinded reviewer if a definitive response assessment can be justified, based on the available information.

- **FDG-PET**: can complement CT scans in assessing progression (particularly possible for 'new' disease). New lesions on the basis of FDG-PET imaging can be identified according to the following algorithm:
  - Negative FDG-PET at baseline, with a positive FDG-PET at follow-up is a sign of PD based on a new lesion.
  - No FDG-PET at baseline with a positive FDG-PET at follow-up:

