# 14.3.10 Determination of non-target lesion response

Table 18: Response criteria for non-target lesions

Response Criteria	Evaluation of non-target lesions	
Complete Response (CR):	Disappearance of all non-target lesions. In addition, all lymph nodes assigned a non-target lesions must be non-pathological in size (< 10 mm short axis)	
Progressive Disease (PD):	Unequivocal progression of existing non-target lesions. 	
Non-CR/Non-PD:	Neither CR nor PD	
Unknown (UNK)	Progression has not been documented and one or more non-target lesions have not been assessed or have been assessed using a different method than baseline.	

Although a clear progression of non-target lesions only is exceptional, in such circumstances, the opinion of the treating physician does prevail and the progression status should be confirmed later on by the review panel (or study chair).

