# Notes on non-target lesion response

- The response for non-target lesions is **CR** only if all non-target non-nodal lesions which were evaluated at baseline are now all absent and with all non-target nodal lesions returned to normal size (i.e. < 10 mm). If any of the non-target lesions are still present, or there are any abnormal nodal lesions (i.e. ≥ 10 mm) the response can only be '**NonCR/Non-PD**' unless any of the lesions was not assessed (in which case response is **UNK**) or there is unequivocal progression of the non-target lesions (in which case response is **PD**).
- Unequivocal progression: To achieve "unequivocal progression" on the basis of non-target disease there must be an overall level of substantial worsening in non-target disease such that, even in presence of CR, PR or SD in target disease, the overall tumor burden has increased sufficiently to merit discontinuation of therapy. A modest

"increase" in the size of one or more non-target lesions is usually not sufficient to qualify for unequivocal progression status. The designation of overall progression solely on the basis of change in non-target disease in the face of CR, PR or SD of target disease is therefore expected to be rare. In order for a PD to be assigned on the basis of non-target lesions, the increase in the extent of the disease must be substantial even in cases where there is no measurable disease at baseline. If there is unequivocal progression of non-target lesion(s), then at least one of the non-target lesions must be assigned a status of "Worsened". Where possible, similar rules to those described in Section 14.3.10 (Determination of target lesion response) for assigning PD following a CR for the non-target lesion response in the presence of non-target lesions nodal lesions should be applied.

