The overall observation period will be divided into three mutually exclusive segments:

pre-treatment period: from day of subject's first informed consent to the day before first administration of study treatment

on-treatment period: from date of first administration of study treatment to 30 days after date of last actual administration of any study treatment (including start and stop date).

post-treatment period: starting at Day 31 after last administration of study treatment in the single arm.

If dates are incomplete in a way that clear assignment to pre-, on-, post-treatment period cannot be made, then the respective data will be assigned to the on-treatment period.

Safety summaries (tables, figures) include only data from the on-treatment period with the exception of baseline data which will also be summarized where appropriate (eg, change from baseline summaries). In addition, a separate summary for death including on-treatment and post treatment deaths will be provided. Summary tables for adverse events (AEs) will summarize only on-treatment events, with a start date during the on-treatment period (***treatment-emergent AEs***).

2.1.1.6 *Handling of Missing Values/Censoring*

Subjects who are of unknown clinical response or not assessed will be treated as nonresponders in the analyses of overall response rate (ORR).

Subjects who haven't experienced the specified event at the time of analysis will have time-to-event data (eg, progression-free survival, overall survival, etc.) censored at the time of last measurement prior to the data cut-off point used in the report.

2.2 *Analysis Sets*

2.2.1 *Full Analysis Set*

The Full Analysis Set (FAS) includes all subjects who received at least one dose of infigratinib. Unless otherwise specified, all the analyses will be done separately for each cohort.

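### Table 19 gives no overall PR or SD when a non-target lesion is unassessed, and an accepted contrast-related imaging switch defaults to UNK; both could lower the central-review ORR

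*Protocol*

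**What the plan says.** **Table 19.** Overall PR requires target PR, no new lesion and a non-target response that is "Non-PD and not UNK". Overall SD carries the same condition. Target CR with non-target UNK and no new lesion is scored PR. There is no row for target PR with non-target UNK, or for target SD with non-target UNK.

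**When the non-target response is UNK.** Table 18 (Section 14.3.10) assigns UNK when progression is not documented and "one or more non-target lesions have not been assessed or have been assessed using a different method than baseline". The notes below it say the same for an incomplete non-target assessment: the response is non-CR/non-PD "unless any of the lesions was not assessed (in which case response is" UNK).

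**Imaging switch.** For a contraindication to CT contrast, Section 14.3.3 accepts "a noncontrast CT of chest (MRI not recommended due to respiratory artifacts) plus contrast-enhanced MRI of abdomen and pelvis" at follow-up. Its next bullet counts any change in contrast use or technique as a change in methodology and says: "A change in methodology will result by default in a UNK overall lesion response assessment". It then lets the investigator or the central blinded reviewer replace that sponsor-calculated UNK when a definitive response can be justified. For the same patients, Section 7.2.1 says "a contrast-enhanced MRI (if possible) of chest, abdomen, and pelvis should be performed".

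**Analysis.** SAP 2.1.1.6: "Subjects who are of unknown clinical response or not assessed will be treated as nonresponders in the analyses of overall response rate (ORR"). SAP 2.6 defines the primary endpoint as central-review ORR based on confirmed CR or PR, and counts any confirmed response before the cutoff and before new therapy. Section 7.2.1 sets confirmation at 4 to 6 weeks. Section 14.3.12 counts an unconfirmed PR as SD.

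**The concern.** Table 19 is inconsistent with itself. It accepts an incomplete non-target assessment when the target lesions have disappeared, and offers no PR or SD outcome when they have shrunk by 30% or stayed stable. Whoever programs or reads such a scan must invent the outcome, and UNK is the likely choice because no other row fits.

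The trigger is low: one unassessed lesion is enough. It is also foreseeable. Section 7.2.1 ties repeat bone imaging for skeletal lesions not visible on the body scans to the 8-weekly timepoints. Confirmation scans fall between those timepoints, and the text does not say whether bone imaging is repeated then.

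The switch rule has a similar defect. The protocol accepts a change of modality and then, by default, withholds a response from the resulting scan. Its only criterion for lifting the default is that another assessment can be justified.

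At stake is whether some real responses go unconfirmed in the primary endpoint, through wording rather than tumour behaviour.

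**Working it through.** **1. The plan's own figure.** Protocol 10.8.1 and SAP 3.1 give maximum half-widths of the exact 95% CI for ORR. Maximising the Clopper-Pearson half-width over all possible responder counts gives 9.87% at 53/106 (stated limit 10%) and 12.02% at 36/72 (stated limit 12%, met after rounding). These hold whatever ORR is observed, so the present point does not alter them. It acts on the point estimate.

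**2. Table 19, rows with no new lesion and no progression.**

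| Target | Non-target fully assessed | Non-target UNK |
|---|---|---|
| CR | CR, or PR if non-target is non-CR/non-PD | PR |
| PR | PR | no row |
| SD | SD | no row |
| UNK | UNK | UNK |

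Two cells are undefined. The one sentence in Section 14.3.12 that forces an unknown status for an unassessed lesion is about target lesions: "If the evaluation of any of the target lesions identified at baseline could not be made during follow-up, the overall status must be 'unknown". It does not fill these cells.

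**3. The switch.** A contraindication known at baseline involves no change from the baseline method, so the default does not apply. One that develops on study does involve a change, in contrast or technique, whether the site follows 7.2.1 or 14.3.3.

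**4. Route to ORR.** Suppose PR is first seen at a scheduled scan and the confirmation scan at 4 to 6 weeks is UNK or unclassifiable. The next scheduled scan is nominally 8 weeks after the first. Using both 7-day windows in full, the gap shrinks to 56 − 14 = 42 days, which only just reaches 6 weeks. Normally it falls outside the window. Neither document says whether a later scan can confirm across an intervening UNK. If it cannot, the PR becomes SD. An affected response scan is similar: the first PR cannot be recorded there.

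**5. Size.** Inputs: n = 106 (Protocol 10.8.1); the true number of responders and the share lost are assumptions, because the documents give neither.

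Per responder lost: 1/106 = 0.94 points (1/72 = 1.39 points in the first interim set). Three lost: 3/106 = 2.83 points.

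Observed ORR = (true responders − lost)/106, with counts rounded to whole patients:

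| True responders (ORR) | 5% lost | 10% lost | 20% lost |
|---|---|---|---|
| 16 (15.1%) | 15 (14.2%) | 14 (13.2%) | 13 (12.3%) |
| 24 (22.6%) | 23 (21.7%) | 22 (20.8%) | 19 (17.9%) |
| 32 (30.2%) | 30 (28.3%) | 29 (27.4%) | 26 (24.5%) |
| 42 (39.6%) | 40 (37.7%) | 38 (35.8%) | 34 (32.1%) |

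The fall runs from 0.9 to 7.5 points over these assumptions, and is zero if no responder is affected.

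**The case against.** Several stronger readings are tempting, and the documents do not support them.

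- *Table 19 declares these scans unknown.* It does not. PR+UNK and SD+UNK are undefined. The table does withhold PR and SD through its explicit exclusion of UNK. A footnote marker on the PR rows has no identifiable text in the extracted document, so a qualification there cannot be ruled out.
- *An accepted switch is UNK whatever the justification.* The words about justification belong to the definition of a contrast change, not to its consequence. The consequence can be overridden.
- *The override exposes the primary endpoint to open-label discretion.* For central-review ORR the reader is the central reviewer, whom Section 14.3.3 describes as blinded. What is missing is a set of criteria.
- *One UNK scan makes a non-responder.* SAP 2.1.1.6 works per subject, and a response confirmed on other scans still counts.
- *PFS and DOR lose assessments.* The SAP censors at the last valid or adequate assessment without saying whether a UNK scan qualifies, so this is not shown.

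Two further points stand. Central reading details are deferred to the imaging CRO's manual, which is not among the documents and may settle both cases. And any loss is conservative for a single-arm estimate with no formal threshold in Cohort 1. Losses of one to three responders (0.94 to 2.83 points) also lie well inside the 9.87-point maximum half-width. None of this removes the inconsistency in the protocol's own table, with which the manual would have to agree.

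**Conclusion.** The point holds as an inconsistency and gap in the response rules, not as demonstrated bias. Target PR or SD with one unassessed non-target lesion has no permitted PR or SD outcome, while target CR in the same situation is scored PR. A switch the protocol accepts is UNK by default, subject to an override with almost no criteria. Sections 7.2.1 and 14.3.3 contradict each other on chest imaging.

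The effect on central-review ORR can only be downward: 0.94 points per affected responder at n = 106. It requires that the response or confirmation scan is affected, that the gap or default is resolved as UNK, and that no other pair of scans confirms the response. The total cannot be derived from the documents. It should be corrected because it touches the primary endpoint and the repair is small.

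**What to change.** 1. Add two rows to Table 19: target PR, non-target UNK, no new lesion = PR; target SD, non-target UNK, no new lesion = SD. Both agree with the existing CR row.
2. State in Section 14.3.3 that the switch it already accepts is not UNK by default when all target lesions remain measurable.
3. Reconcile Sections 7.2.1 and 14.3.3 on chest imaging. Which modality is right is for the clinical and imaging teams.
4. State whether a response can be confirmed across an intervening UNK scan.
5. Apply the same rules in the sponsor's derivation and the central reading rules.
6. Add an ORR sensitivity analysis that scores these scans as UNK. It shows how many PR or SD calls rest on incompletely assessed non-target disease, which is the small downside of items 1 and 2.

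The cost is appendix wording, one programming rule and one extra table; no extra scans. The first formal Cohort 1 interim analysis has already been done and the change can only leave ORR the same or raise it. It should therefore be dated, and both results reported.

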# 14.4 Appendix 4: FGFR1/2/3 Allowed Mutations (Known Activating Mutations)

Patients who have a mutation listed below meet the inclusion criterion 2c.

FGFR Mutation	Functional Effect
FGFR1 N546K	Activating
FGFR1 K656E	Activating
FGFR2 S252W	Activating
FGFR2 P253R	Activating
FGFR2 A315T	Activating
FGFR2 Y375C	Activating
FGFR2 C382R	Activating
FGFR2 N549K	Activating
FGFR2 K659E	Activating
FGFR3 R248C	Activating
FGFR3 S249C	Activating
FGFR3 G370C	Activating
FGFR3 S371C	Activating
FGFR3 Y373C	Activating
FGFR3 G380R	Activating
FGFR3 K650E	Activating
FGFR3 K650M	Activating

Sources: Helsten 2015, data on file.

# 14.5 Appendix 5: List of Highly Effective Methods of Contraception

The following is from the Clinical Trials Facilitation Group 2014 (Section 4.1).

Methods that can achieve a failure rate of less than 1% per year when used consistently and correctly are considered as highly effective birth control methods. Such methods include:

•	combined (estrogen and progestogen containing) hormonal contraception associated
	with inhibition of ovulation  .

- o oral
- o intravaginal
- transdermal
- progestogen-only hormonal contraception associated with inhibition of ovulation :
  - o oral
  - o injectable
  - o implantable 
- intrauterine device (IUD) 
- intrauterine hormone-releasing system (IUS) 
- bilateral tubal occlusion 
- vasectomised partner 
- sexual abstinence 

- 2 Contraception methods that in the context of this guidance are considered to have low user dependency.
- 3 Vasectomised partner is a highly effective birth control method provided that partner is the sole sexual partner of the WOCBP trial participant and that the vasectomised partner has received medical assessment of the surgical success.
- 4 In the context of this guidance sexual abstinence is considered a highly effective method only if defined as refraining from heterosexual intercourse during the entire period of risk associated with the study treatments. The reliability of sexual abstinence needs to be evaluated in relation to the duration of the clinical trial and the preferred and usual lifestyle of the subject.

 Hormonal contraception may be susceptible to interaction with the IMP, which may reduce the efficacy of the contraception method (see Clinical Trials Facilitation Group 2014, section 4.3).

- Change the term of 'patient' to 'subject' as appropriate
- Change the term of 'BGJ398' to infigratinib as appropriate
- Change the term of FMI v1 and FMI v3 to FMI I and FMI III, respectively
- Update the Protocol table/section numberings cited in this SAP to match with the corresponding tables/sections in the protocol
- Remove all the analyses related to the Bayesian approaches.

Changes to specific sections

- Title page: update SAP version set to Final V1.0 and update the date
- Study design, Study objectives and endpoints: updated to match with the protocol amendment 4 (24-Apr-2019)
- Data analysis general information: updated to match with the protocol on the scope and timing for the interim, primary and final analyses
- Investigational drug and study treatment: updated to match with the protocol on the introduction of new formulation of FMI IV; indicate that the analysis by treatment/formulation is determined by formulation a subject first received if a subject switches formulation during the study as required per the Protocol
- Analysis sets: clarify how analysis will be organized within Full Analysis Set (by treatment, by FGFR2 fusion/translocations status, etc); remove the Safety Set since it is overlapped with

the Full Analysis Set; clarify the definition of Per-Protocol Set; remove the section of Patient Classification; add Interim Analysis Set for Cohort 1 and Interim Analysis Set for Cohort 3; remove the section of Withdrawal of Informed Consent since it is not an analysis set; provide details on Subgroup of interest

- Subject disposition: clarify the summaries which will be provided for subject disposition.
- Demographic: The category of ‘18 - <65 years, 65 - <85 years and \geq 85 years’ is replaced with ‘<65 years vs \geq 65 years’
- Prior antineoplastic therapy: clarify the summaries which will be provided for prior antineoplastic therapy
- Protocol deviations: clarify the categories of protocol deviations
- Study Treatment: indicate that no study treatment permanent discontinuation will be discussed in this section; remove several sections which provide too detailed programming specification; clarify the definition of treatment duration and relative dose intensity; specify that no summary will be provided for planned dose intensity and actual dose intensity; simply the algorithm for the summary of dose reductions and interruptions
- Prior, concomitant and post therapies: specify only on-treatment concomitant medication will be summarized; no general listing for concomitant will be provided.
- Compliance: the category of ‘< 0.5, \geq 0.5 - < 0.75, \geq 0.75 - < 0.9, \geq 0.9 - < 1.1 and \geq 1.1’ is replaced with ‘< =0.5, > 0.5 - <= 0.75, > 0.75 - <= 0.9, > 0.9 - <= 1.0 and >1.0’
- Analysis of the primary objective: specify that ORR per central review imaging will be the primary endpoint; clarify the timing for the interim and primary analysis for Cohort 1; delete all the analyses using Bayesian approaches; delete the subsection of Supportive analyses
- Analysis of secondary objective(s): update to be consistent with the Protocol Amendment 4; add the description on best tumor burden change; provide details on the PFS censoring specification; provide the details on PFS sensitivity analysis; introduce the definition of PFS > 16 weeks for Cohort 2 and Cohort 3;
- Safety objectives: specify ‘In general, summary will be provided only for the on-treatment safety assessments, which are the assessments occurring or taken during the on-treatment period’
- Adverse Events: emphasize that only TEAEs will be summarized; removed the summary tables related to TEAEs leading to study discontinuation; added some summary tables for TEAE; add the description of Adverse Events of Special Interest for this study
- Laboratory data: minor update on Table 2-3 and 2-4 and indicate the laboratory tests in those two tables are just examples; clarify the details on how laboratory data will be analyzed

- Other safety data: Add sections on Ophthalmologic assessment and Left ventricular ejection fraction (LVEF); clarify the analyses of ECG and cardiac imaging data and vital signs and ECOG performance status; for tolerability, the category of ‘<0.5, ≥0.5 - <0.75, ≥0.75 - <0.9, ≥0.9 - <1.1 and ≥1.1’ is replaced with ‘<=0.5, >0.5 - <=0.75, >0.75 - <=0.9, >0.9 - <=1.0 and >1.0’
- Pharmacokinetics: update to indicate FMI IV will be used; Clarify that the sections on the PK analysis is intended to provide general principle for the PK analysis. Additional details of the analysis approaches will be provided in a separate PK analysis plan
- Exploratory analyses: indicate that the exploratory analyses will be conducted if there are sufficient data available
- Interim Analysis: specify the interim analysis for Cohort 1 and the interim analysis for Cohort 3
- Sample size calculation: update the rationale for Cohort 1 sample size based estimation precision (the Bayesian approach is removed); add the rationale for Cohort 2 and Cohort 3 sample size
- Imputation rules: Clarify the imputation rules for AE and CM start/end partial/complete missing date and the scope of the application of the imputation rules

SUMMARY OF CHANGES (V2.0, Amendment 1)

This Summary of Change summarized the change of the Statistical Analysis Plan Version 2.0 for Study CBGJ398X2204 from Version 1.0 (29 May 2019).

Rationale for Change

The primary purpose of the changes is to:

- Revise the SAP to be consistent with the Protocol Version 6 (Amendment 5) (15-Jan-2020)

Global Changes

- Change the term of 'BGJ398' to infigratinib as appropriate

Description of Changes

- Title page: update SAP version and date and the corresponding protocol version and date
- Approval signature page: removed and a separate signature page will be used for approval
- List of Abbreviations: Add CSR/RPED
- 1 Introduction: update the corresponding protocol version and date
- 1.1 Study design: update to match with the current protocol
- Table 1-1: update to match the protocol
- Figure 1-1: replace with the one in the current protocol and the main change is from 'Cohort 1: ~120 patients, 108 with FGFR2' to 'Cohort 1: ~120 patients, 106 with FGFR2'
- 2.1 Data Analysis General Information: replace 'QED personnel' with 'QED Therapeutics'; indicate that one additional interim analysis will be added for Cohort 1; add details of the data review for Cohort 2 and Cohort 3
- 2.1.1.1 Investigational Drug and Study Treatment: add 'if subjects without FGFR2 fusion/translocation are included in the analysis' to clarify analysis details since only subjects with FGFR2 fusion/translocation will be included for the second formal interim analysis for Cohort 1.
- 2.2 Analysis Sets: update analysis sets used for the analyses mainly due to the change of adding the second interim analysis for Cohort 1
- 2.2.8 Subgroups of Interest: clarify the subgroups related to CYP3A4 inhibitors

- 2.3.3 Medical History: indicates a summary table of medical history will be provided instead of a listing.
- 2.4 Protocol Deviation: add ‘Unless otherwise specified’ since FAS will not be used for the second interim analysis for Cohort 1 after amendment 3
- 2.6 Analysis of Primary Objective: remove ‘using FAS, or Interim Efficacy Analysis Set for Cohort 1’ since different analysis sets will be used for different interim/primary/final analyses
- Best Overall Response and Disease Control in 2.7.1: add ‘as specified by Cohort (Section 2.1)’
- 2.7.2 Safety Objectives: clarify the analysis sets which will be used for safety summary and listings.
- Deaths in 2.7.2.1.2: remove ‘for the full analysis set’ since the details on which analysis sets should be used for death listings have been clarified in the section of ‘Safety Objective’
- Adverse Events of Special Interest in 2.7.2.1.2: to match the program wide definition: update the adverse events of special interest; add the section for ‘Minimum Critical Toxicities’; add the section of ‘phosphate binders medication’
- 2.7.2.2.1 CTC Grading for Laboratory Parameters: add details to clarify how grade 0 will be assigned.
- 2.7.2.2.1 Imputation Rules: clarify the algorithm of corrected calcium
- 2.7.2.2.3. Data Analysis: add ‘as discussed in Minimum Critical Toxicities in Section 2.7.2.1.2’ to provide analysis reference
- Table 2-3 Example of Laboratory Parameters for Which CTCAE Grades are Defined: update the table to be consistent with the analysis approaches
- Table 2-4 Examples of Laboratory Parameters (Without CTCAE Grades) for Which Lab Reference Ranges are Defined: update the table to be consistent with the analysis approaches
- 2.7.3 Other Safety Data: add a paragraph to provide overall guidance on the analysis
- 2.7.3.4 Vital Signs and ECOG Performance Status: clarify the summary of ECOG
- 2.7.4 Pharmacokinetics: replace “pre-dose and 2-hr post-dose” with “trough and 2-hour or 4-hour”; change ‘Table 9 of CSP Amendment 4’ to ‘Table 10 of CSP Amendment 5’
- 2.7.4.3 Analysis Sets: Details added to match with the protocol
- 2.7.4.4 Basic Tables, Figures and Listings: Details added to match with the protocol

- Table 2-6 Non-compartmental pharmacokinetic parameters: update the table to match the protocol amendment 5
- 3.8.1.3.1 Analysis Sets: the section numbering is corrected to be 2.8.1.3.1; add ‘unless otherwise specified’
- 2.9 Interim Analysis: update the details of the interim analyses to match with the protocol amendment 5
- 3.1 Cohort 1: Two subjects who were considered previously as FGFR2 fusion/translocation subjects do not actually have FGFR2 fusion/translocation. Therefore, the number ‘74’ is changed to ‘72’ and ‘108’ is changed to ‘106’
- 5 Appendix: Add the following contents
- Table of Adverse Events of Special Interest, Search Strategies, and Rationales for Sponsor-Defined Search Strategies
- AESI: Calcium-phosphate homeostasis – hypercalcaemia, hyperphosphataemia and hypophosphataemia
- AESI: Eye Disorder of Central Serious Retinopathy/Retinal Pigment Epithelium Detachment
- AESI: Pathological Fracture
- AESI: Tissue Calcification
- AESI: Vascular Calcification / Mineralization
- AESI: Eye Disorder: SOC Eye Disorders (Excluding 9 PTs Used to Characterize CSR/RPED)
- Minimum Critical Toxicities
- CYP3A4 Inhibitors and Inducers
- Phosphate Binders
- 6 Reference: add one more reference

SUMMARY OF CHANGES (V3.0, Amendment 2)

This Summary of Changes summarized the change of the Statistical Analysis Plan Version 3.0 for Study CBGJ398X2204 from Version 2.0 (26 March 2020).

Rationale for Change

The primary purpose of the changes is to:

- More precisely specify analysis methods for overall response rate (ORR), time to response (TTR), and duration of response (DOR).

Description of Changes

- Title page: updated SAP version, amendment number, and date; replaced ^{PI} with ^{PI}
- Summary of Changes: Added version and amendment numbers for clarity, as appropriate.
- Section 2.6.1: Added paragraph to specify analysis methods.
- Section 2.6.2: Removed the last sentence (related to Section 2.6.1 change above).
- Section 2.7.1: Added paragraph to specify analysis methods and deleted last sentence.
- Throughout: Reformatted to be in the current QED template and style guide, including revising table and figure numbers, adding appropriate headings to appear in the Table of Contents (eg, List of Abbreviations, Summary of Changes), completing the List of Abbreviations, defining abbreviations on first use only, appropriately referring to sections, and other minor editorial/administrative changes.

LIST OF ABBREVIATIONS

| | |
|----------|---|
| AE | adverse event |
| AESI | adverse event of special interest |
| ATC | Anatomical Therapeutic Chemical |
| AUC | area under the curve |
| bid | bis in diem/twice a day |
| BLQ | below the limit of quantitation |
| BOR | best overall response |
| cfDNA | cell-free DNA |
| CI | confidence interval |
| CR | complete response |
| CSR | Clinical Study report |
| CSR/RPED | central serious retinopathy/retinal pigment epithelium detachment |
| CTC | Common Toxicity Criteria |
| CTCAE | Common Terminology Criteria for Adverse Events |
| DOT | duration of response |
| FAS | full analysis set |
| eCRF | electronic Case Report Form |
| LVEF | left ventricular ejection fraction |
| MedDRA | Medical Dictionary for Drug Regulatory Affairs |
| NCI | National Cancer Institute |
| o.d. | once daily |
| ORR | overall response rate |
| OS | overall survival |
| PD | pharmacodynamics |
| PFS | progression-free survival |
| PK | pharmacokinetics |
| PPS | per-protocol set |
| PR | partial response |
| PT | Preferred Term |
| qd | qua'que di'e / once a day |
| RECIST | Response Evaluation Criteria in Solid Tumors |
| SAE | serious adverse event |
| SAP | Statistical Analysis Plan |
| SD | standard deviation |
| SOC | System Organ Class |
| SMQ | Standardized MedDRA Queries |
| TEAE | treatment-emergent adverse event |
| TFLs | tables, figures, listings |
| TTR | time to response |
| WHO | World Health Organization |

